Recent studies have demonstrated that NAC can blunt tissue oxidative stress and decrease insulin resistance [11, 12]. Preclinical studies in our laboratory have also demonstrated that NAC can augment tissue perfusion and arterial collateral maturation (arteriogenesis) in a novel murine hind limb ischemia – amputation model, as well as alter the phospholipid profile in vascular endothelial cells. Recent clinical trials have repeatedly demonstrated the safe administration of NAC [8-10]. **We therefore hypothesize that perioperative administration of NAC in patients with CLI, with and without diabetes, who are undergoing major lower extremity amputation will improve tissue stump perfusion and alter tissue lipidomics.**

Primary Hypothesis

Our primary hypothesis is that perioperative administration of NAC in patients with CLI, plus or minus diabetes, who are undergoing major lower extremity amputation will improve tissue stump perfusion and alter tissue lipidomics, ultimately reducing amputation associated morbidity with respect to wound breakdown, wound infection, and amputation revision.

Purpose of the Study Protocol

The purpose of this study protocol is to evaluate the safety and potential efficacy of NAC in the setting of peripheral arterial disease as a tissue augmentation agent in patients with CLI undergoing lower limb amputation. This will be a Pilot Clinical trial designed to facilitate a future power calculation for a larger, likely multicenter trial that can evaluate the potential clinical benefit of using NAC to improve healing and perfusion of amputation stumps in diabetic patients.

This study is highly innovative in that it will: i) explore a compelling new modality of therapy in a highly vulnerable, but frequently under-represented clinical trial patient population, and ii) represent the potential use of a low-cost, generic, well-established, and generally very safe pharmacological agent for an important clinical problem. This would otherwise not be pursued by drug pharmaceutical manufacturers due to anticipated low-profit margins from a generic pharmacological agent.

Background

Prior Literature and Studies

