Aside from smoking cessation and physical exercise, there are currently no known effective medical treatments for patients with advanced non-surgically correctable CLI [13, 21]. In addition, the prevalence of amputations resulting from CLI among diabetic patients is disturbingly high [2]. Based on our recent preclinical studies, we are proposing a pilot clinical trial to further explore the potential therapeutic benefits of NAC in healing extremity amputation stumps in the setting of CLI, plus or minus diabetes. These studies are highly innovative in that they: i) explore a compelling new modality of therapy in a highly vulnerable, but frequently under-represented clinical trial patient population, ii) explore a completely novel and not previously reported NAC mechanism of action on phospholipid synthesis and expression, and iii) represent the potential use of a low-cost, generic pharmacological agent, which would otherwise not be pursued by drug pharmaceutical manufacturers due to low-profit margins. In short, this proposal may establish a conceptual infrastructure for future larger clinical trials exploring the use of NAC in patients with CLI and with and without diabetes, and identify a previously unknown novel mechanism of action for NAC.

We believe that previous literature supporting the role of NAC in augmenting compensatory tissue perfusion raises the possibility that this may be an advantageous therapeutic agent to favorably alter the tissue lipidomic profile of diabetic patients receiving NAC. We believe that NAC offers a new treatment strategy for patients with CLI undergoing lower extremity amputation with the intent to improve tissue perfusion, healing, and reduce morbidity and mortality associated with lower limb amputation.

Study Objectives

Primary Aim 1

Determine whether NAC can affect major lower extremity amputation stump perfusion by POD (Post-operative Day) 5

Primary Aim 2

Determine whether NAC can affect major lower extremity stump healing for 30 days following amputation.

Secondary Aim

Determine the effect size in diabetic patients that is necessary to power a larger clinical trial to determine whether NAC treatment can improve tissue perfusion and healing at major lower extremity amputation stumps.

Rationale for the Selection of Outcome Measures

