In this pilot clinical study we propose to conduct a prospective, randomized, double-blinded, placebo-controlled clinical trial, in 50 human subjects with CLI who have undergone a major (above-knee or below-knee) lower extremity amputation. 25 patients will receive NAC 1200mg intravenously twice a day for 6 consecutive days following amputation. 25 patients will receive placebo saline intravenous infusion twice a day for 6 days following amputation. Post-amputation patients will be monitored for specific anthropometric parameters and stump perfusion assessments (using laser-assisted fluorescent angiography and transcutaneous oxygen pressure measurement). **The primary study endpoints are to determine if lower extremity stump healing and perfusion are affected by perioperative NAC administration. A secondary endpoint will be to determine the effect size that would be necessary to power a larger clinical trial to determine whether NAC treatment can affect tissue perfusion and healing at major lower extremity amputation stumps in patients with CLI.**

Subject Selection and Withdrawal

Inclusion Criteria

Inclusion criteria for recruited subjects will be as follows:

- Subject undergoing elective major (above-knee or below-knee) lower extremity amputation for CLI
- Both male and female patients
- All ethnic groups
- Between of the ages of 30-90 years old

1.a Exclusion Criteria

Exclusion criteria for patients will be as follows:

- Pregnant women, and women who are breastfeeding
- Known history of end-stage liver disease
- Severe asthma
- Heavy alcohol consumption (male > 2 drinks per day and women > 1 drink per day)
- Individuals actively receiving chemotherapy.

- Anticipated enrollment in another study that investigates another drug agent within 30 days from enrollment in this study.
- Patients receiving carbamazepine.
- Severe anemia (HCT < 22).
- Allergy to either NAC or ICG

All inclusion and exclusion criteria will be verified from patient chart in Epic and through self report and/or LAR report; in particular, alcohol consumption and participation in another drug research study to obtain the most current information. **Email correspondence between RC, PI, and other study team members regarding patient enrollment may be included in the subjects chart to serve as a real time documentation of PI's approval to enroll participant, in addition to signature in CRFs.**

Ethical Considerations

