Upon consent and enrollment in the study, relevant subject information will be relayed to the Barnes Jewish Hospital (BJH) Investigational Pharmacy. Prior to proceeding to the operating room for lower extremity amputation, the patients will be randomized 1:1 by the BJH Investigational Pharmacy to either placebo saline infusion (twice daily) or a standard adult intravenous dose of NAC (1200mg twice daily) for 6 days post-amputation during the usual post-operative inpatient extremity off-loading and stump monitoring period. The pharmacy will maintain blinding, with no member of the investigational team having access to the record until the conclusion of the trial.

Early Withdrawal of Subjects

Patients unable to tolerate the administration of the drug will be withdrawn from the study at any point during their hospitalization and will continue to be monitored until their condition stabilizes. Patients unable to participate in the Post-operative Day 0 Non-invasive Laser Assisted Fluorescence Angiography (LAFA) will be withdrawn from the study at that time point and will not receive the investigational product. Subjects for which continuous IV access is not medically indicated during the 6 day study drug administration period may be withdrawn from the study. Patients unable to participate in follow-up appointments will also be withdrawn from the study.

When and How to Withdraw Subjects

Patients unable to tolerate the administration of the drug will be withdrawn from the study trial at any point during their hospitalization. Patients unable to participate in follow-up appointments will also be withdrawn from the study. They will continue to be monitored for adverse events as inpatients for the duration of their hospitalization. Patients unable to participate in the Post-operative Day 0 Non-invasive Laser Assisted Fluorescence Angiography (LAFA) will be withdrawn from the study at that time point and will not receive the investigational product. No further study follow up will be required.

Data Collection and Follow-up for Withdrawn Subjects

Patient data will be collected up until time of withdrawal from the study and pooled into the collective analysis along with all other patients.

Study Drug

Description

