N-acetyl cysteine (NAC) ((2R)-2-acetamido-3-sulfanylpropanoic acid) is an amino acid derivative of L-cysteine, which is a precursor to glutathione and cysteine. Historically, NAC has been used to treat acetaminophen overdose [6], as well as mucous secretions in patients with cystic fibrosis or chronic obstructive pulmonary disease [24].

Pharmacokinetics including the following [24] :

Distribution: The steady-state volume of distribution (V_{dss}) and the protein binding for acetylcysteine were reported to be 0.47 liter/kg and 83%, respectively.

Metabolism: N-acetyl-cysteine may form cysteine, disulfides, and conjugates in vivo (N, N'-diacetylcysteine, N-acetyl cysteine-cysteine, N-acetyl cysteine-glutathione, N-acetyl cysteine-protein, etc). Based on published data, it was reported that after an oral dose of 35S-acetylcysteine, about 22% of total radioactivity was excreted in urine after 24 hours. No metabolites were identified.

Elimination: After a single intravenous dose of N-acetyl cysteine, the plasma concentration of total N-acetyl cysteine declined in a poly-exponential decay manner with a mean terminal half-life (T_{1/2}) of 5.6 hours. The mean clearance (CL) for N-acetyl cysteine was reported to be 0.11 liter/hr/kg and renal CL constituted about 30% of total CL.

Treatment Regimen

Upon study enrollment, patients will be randomized 1:1 by BJH Investigational Pharmacy to either placebo ½ normal saline infusion (twice a day) or a standard adult intravenous dose of NAC (1200mg twice a day) for 6 days post-amputation. The BJH Investigational Pharmacy will perform this with knowledge of the patient's medical record number (MRN), and without knowledge of any pre-existing medical conditions, comorbidities, past medical history, prior interventions, etc. The first infusion will be administered within three hours from leaving the operating room. The second infusion will be a minimum of 6 hours after the first infusion, or at 21:00 in an attempt to be consistent with routine hospital BID dosing times. Patients will receive their scheduled infusions as long as they are hospitalized according to the chart below (Table 1). **If medication is not administered within that window, dose will not be given to not interfere with the rest of the doses.**

Table 1:

Post-operative Day (POD)	Infusion Schedule
POD 0	1. Within 3 hours from the conclusion of the operation 2. Approximately 6 hours after first infusion, or at 21:00 +/- 6 hours

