One of the main study outcomes (and in the future large study) is the stump perfusion assessment, which is a continuous variable measured three times (D0, D3, and D5) after treatment. Based on this longitudinal repeated measurement study design, the preliminary data needed for designing future study include: (1) variance of single measurement, (2) covariance (correlation) among the repeated measurements over time within an individual, (3) level of outcome measurements in patients with and without the treatment.

Missing Outcome Data

Not applicable

Unblinding Procedures

The BJH Investigational Pharmacy will maintain a record of each patient's medical record number and to which arm of the study they were assigned. No member of the vascular surgery investigational team will have access to this information. This will serve to maintain blinding and reduce any unwanted during the trial and subsequent analysis of collected data. Un-blinding of patient data will occur during the interim analysis, and at the end of the study. For un-blinding the pharmacy will then un-blind the study to the investigators such that appropriate conclusions can be made regarding the efficacy of the investigational agent.

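### The secondary aim asks for an effect size in diabetic patients, but the trial enrols patients with and without diabetes and the planned analysis reports nothing separately for diabetics

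*Combined protocol and SAP*

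**What the plan says.** **The aim.** Under Study Objectives, the protocol's Secondary Aim is to "Determine the effect size in diabetic patients that is necessary to power a larger clinical trial". Purpose of the Study Protocol likewise describes the later trial as one in diabetic patients.

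**Who is enrolled.** The Primary Hypothesis concerns "perioperative administration of NAC in patients with CLI, plus or minus diabetes". The first inclusion criterion is "Subject undergoing elective major (above-knee or below-knee) lower extremity amputation for CLI". Diabetes is neither required nor given a target number.

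**The same endpoint elsewhere.** The Overview or Design Summary also makes the effect size a secondary endpoint, but for "tissue perfusion and healing at major lower extremity amputation stumps in patients with CLI", with no restriction to diabetes. Rationale for the Selection of Outcome Measures gives the effect-size goal without mentioning diabetes. Rationale for this Study foresees larger trials in CLI with and without diabetes.

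**The analysis.** The Statistical Plan (protocol, repeated in the SAP) partitions variance, estimates the intra-class correlation, and compares the two treatment groups by GEE or a mixed model. The planning inputs listed under Statistical Methods are variance, correlation and "level of outcome measurements in patients with and without the treatment". No diabetic subgroup, diabetes covariate or interaction is named. The data analysis paragraph under Anthropometric Measurements relates those data to healing and perfusion, which is not a treatment effect in diabetics.

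**Use of the effect size.** Sample Size Determination and Power says that effect size should rest on the minimum clinically important difference and not on the pilot, although the pilot may suggest what is achievable.

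**The concern.** The stated purpose of this pilot is to supply design inputs for a larger trial. If that trial is in diabetics, pooled inputs serve it only when the treatment effect, SD and correlation are the same in non-diabetics. The protocol gives reasons to doubt this. Its Background describes impaired collateral formation and stump healing in diabetes, and its preclinical amputation study used diabetic mice.

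At stake is whether the later trial is designed on figures from the wrong population. The error could run either way: a pooled effect smaller than the diabetic one makes the next trial too large, and a larger one makes it too small.

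**Working it through.** **1. The plan's own figure.** 25 + 25 = 50, which agrees with the design summary. With 10% dropout, 25 × 0.9 = 22.5 evaluable per arm. No alpha, power, SD or effect size is given, so the 25 per group cannot be derived further.

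**2. Aim against analysis.**
- Secondary Aim: effect size, diabetic patients.
- Design summary: effect size, all patients with CLI.
- Eligibility: CLI, diabetes not required.
- Statistical Plan: variance, correlation and level by treatment arm, all patients together.
- Sample size section: effect size not to be determined by the pilot.

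The analysis matches the design summary's population but not the Secondary Aim's. The sample size section sits badly with either statement of the endpoint.

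**3. Can diabetes status be obtained?** Yes. Screening for Eligibility records medical history at baseline. HbA1c is optional: it may be obtained when there is no value from the preceding 3 months. History can therefore define the subgroup, and HbA1c can only support it.

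**4. Precision of a diabetic estimate.** The documents give no diabetic share, so 40% to 80% is assumed. Evaluable diabetics per arm are n = 22.5 × share. The 95% half-width for a standardised difference is 1.96 × √(2/n).

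| Share | n per arm | Half-width (SD) |
|---|---|---|
| 40% | 9 | 1.96 × √(2/9) = 0.92 |
| 60% | 13.5 | 1.96 × √(2/13.5) = 0.75 |
| 80% | 18 | 1.96 × √(2/18) = 0.65 |
| Pooled | 22.5 | 1.96 × √(2/22.5) = 0.58 |

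This is a normal approximation for one measurement per patient and an effect near zero. Baseline or repeated measures could change the width, but the documents give no correlation.

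**5. What pooling could do (all inputs assumed).** Take 60% diabetic, an effect of 0.8 SD in diabetics and none in others. The pooled effect is 0.6 × 0.8 + 0.4 × 0 = 0.48 SD. With n per arm = 2 × (1.96 + 0.84)² / d², two-sided 5% and 80% power, d = 0.48 gives 69 per arm and d = 0.8 gives 25. With an effect of 0.4 SD in non-diabetics, the pooled value is 0.6 × 0.8 + 0.4 × 0.4 = 0.64 SD, giving 39 per arm. These figures matter only if the pilot effect is used for sizing, which the sample size section discourages. The SD and correlation would still be needed for the right population.

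**The case against.** **The pooled estimate may be the intended one.** If the design summary reflects the intent, the analysis is right and only the wording of the Secondary Aim needs changing. This stands, and it is why reconciliation comes first. It does not remove the mismatch.

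**A diabetic estimate will be imprecise.** True, as step 4 shows. That is a reason to show the interval, not to leave the estimate out.

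**A stronger reading is tempting.** The Treatment Regimen section has the pharmacy randomise "without knowledge of any pre-existing medical conditions, comorbidities, past medical history, prior interventions, etc", and no stratification factor is named. A reader might infer that randomisation itself defeats the aim or biases the comparison. The documents do not support that.
- A NAC-placebo comparison within diabetics remains a randomised, unbiased comparison under unstratified 1:1 allocation.
- Uneven splits cost little. In simulation of 25/25 allocation, the median loss of precision was under 1%. The 95th percentile was about 7%, 3% and 1% at assumed shares of 40%, 60% and 80%.
- For the pooled comparison, the chance of a gap of 5 or more diabetics between arms of 25 is 16% to 20% (assumed share 70% to 50%). If diabetes shifted perfusion by 0.5 SD (assumed), a 20-point gap would move the difference by 0.20 × 0.5 = 0.10 SD. The standard error is √(2/22.5) = 0.30 SD, so the shift is one third of it. This is chance imbalance, already part of random error, and not systematic bias.

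Stratified blocks in 50 patients are a trade-off that the sponsor may decline. A treatment-by-diabetes term would be uninformative: at an assumed 60% share, with 13.5 and 9 evaluable per arm, its half-width is 1.96 × √(2/13.5 + 2/9) = about 1.2 SD.

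**Conclusion.** The planned analysis does not answer the Secondary Aim as worded, and the documents do not agree on the population or on whether the pilot should supply an effect size. This follows from reading the sections together and needs no assumption. It does not mean that the aim is unanswerable: diabetes status can be taken from baseline history and a subgroup estimate is possible. Nor does it show a fault in the randomisation.

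The numerical size depends on the unstated diabetic share. Between 40% and 80%, the diabetic interval is about ±0.92 to ±0.65 SD, against ±0.58 SD pooled. How far pooled inputs would mislead depends on how much diabetics differ from other patients, on which the documents give no figures.

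**What to change.** 1. Reconcile the Secondary Aim, the design summary and the sample size section. State one target population and say how the pilot effect size will be used.
2. If all patients with CLI are the target, reword the Secondary Aim. The analysis can stay as it is.
3. If diabetics are the target, define diabetes in the SAP from the baseline medical history, with HbA1c as support where available. Report for diabetic patients, beside the pooled figures, the SD, the within-patient correlation, the perfusion level in each arm, and the NAC-placebo difference with its 95% CI.

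Stratified randomisation and a treatment-by-diabetes term are not required for this. The cost is a few more tables, built on history already recorded, and a visibly wide interval for diabetics. The change is best made before the interim analysis, when the plan unblinds the investigators.

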In this pilot clinical study we propose to conduct a prospective, randomized, double-blinded, placebo-controlled clinical trial for 30 days for patients with CLI who undergo a major (above-knee or below-knee) lower extremity amputation. By exploring the primary endpoints we aim to

determine whether NAC can affect amputation stump perfusion and healing. Based on our preclinical data, we hypothesize that NAC will augment both amputation stump perfusion as well as healing. We will utilize the data from this trial to determine the true effect size that is necessary for a larger clinical trial to determine the clinical efficacy of NAC in healing surgical sites such as major lower extremity amputation stumps.

In addition, we will obtain MR perfusion studies on 6 subjects (3 NAC and 3 placebo) conducted at approximately post-operative day (POD) 4. The study team will continue to remain blinded to their study drug randomization. The study pharmacist will notify the study team of which subjects will be eligible to have an MR perfusion study. For example, if the MR perfusion portion of the study has already recruited 3 patients from the NAC group, and the fourth eligible patient also randomizes to NAC, the pharmacy will notify the study team that the patient is not eligible for the MR perfusion study.

MR perfusion studies will be performed by [name] and his research on a Siemens Prisma 3.0 T MR (Software version VE11c (latest software version), 40 mT/meter; 200 μ sec rise time) in CCIR. The subject will lie down on a MRI table and The MRI scan will undergo only at rest. The MR study will be performed without using of any MR contrast media. The scan protocol will involve scout imaging to localize the calf and stump regions. This will be followed by perfusion, diffusion, and oxygenation imaging in these regions. The expected scan time will be less than 45 min.

MR perfusion studies will only be used for research purposes (i.e. will not direct medical/clinical therapy). MR perfusion will be used to assess skeletal muscle perfusion at the healing amputation stump. This data will be used in adjunct to assess overall stump perfusion along with the LAFA studies that are will already be performed on the patient.

Investigational Agent

Preclinical Data

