- **Postoperative Day5:** Obtained at the bedside in the inpatient hospital unless the patient is discharged.

Contraindications to LAFA:

- Patient refusal/inability to precipitate in measurement before or during data collection.

- Allergic reaction previously documented to Indocyanine green (ICG) fluorescent dye (*a contraindication to LAFA does not exclude the patient from other measurements within the study protocol*).
- Patient unable to lie supine and immobile for at least 10 minutes during the imaging procedure.
- End-stage liver disease
- Severe clinical asthma

LAFA Procedural Steps:

1. Each patient is entered into the Novadaq SPY *Elite*[®] computer system, with pre-set optimized settings for appropriate visualization for LAFA.
2. Utilizing a standard protocol per the manufacturer (Novadaq SPY *Elite*[®] system), a 7.5mg (3mL) solution of ICG (reconstituted with sterile saline) is injected intravenously into each patient.
3. The patient is asked to lie supine, immobile for a period of approximately 10 minutes
4. The device is placed over the limb/amputation stump being studied and centered to allow full visualization of the entire stump
 - a. Prop up and immobilize stump
 - b. Obtain a still color image of the stump
 - c. Start an image buffering time of between 10-30 seconds
 - d. ICG is intravenously injected by the patient's nurse or a member of the study team.
 - e. ICG injection is followed by a 10mL of sterile saline flush in the same intravenous line.
 - f. A member of the study team will obtain LAFA imaging of the stump for a total of 150-180 seconds.
 - g. All study images will be stored on the Novadaq SPY *Elite*[®] system hard drive. Study images, including only the study ID and date of exam, will be loaded onto a jump drive and then immediately downloaded onto the WUSTL Department of Surgery/Vascular network drive. The images will then be deleted from the jump drive..
5. Each study patient will be carefully monitored by a physician, nurse practitioner, physician assistant or nurse for signs and symptoms of allergic reaction or intolerance to this non-invasive procedure until discharge.

B. Measurement of Transcutaneous Oxygen Pressure (TcPO₂)

Location of Procedure:

- Barnes-Jewish Hospital Operating Rooms
- 4400/8300/7400/7500 Inpatient Hospital Units
- Other Hospital Units also housing vascular surgery patients

Time of Data Collection:

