2. Clean the selected measuring site with alcohol or other skin-preparation solution.
3. Dry the site well with a gauze pad.
4. Take a standard fixation ring.

5. Remove the fixation ring from the protective film.

6. Apply the fixation ring to the measuring site as follows:
 - Press the center of the fixation ring onto the measuring site with a finger.
 - Run a finger around the rim circumference.

Note: Press firmly to prevent leaks.

7. Fill the hole in the fixation ring with 3-5 drops of the contact liquid.

8. Affix the electrode into the fixation ring as follows:
 - Align the arrow on the electrode with one of the marks on the fixation ring.
 - Turn the electrode 90° clockwise to fasten it in the fixation ring.

9. Repeat steps 1 to 8 if more electrodes are to be applied.

Wait for a stable reading after the electrode has been affixed to the patient.

Note: The physiological stabilization time of a patient is 15-20 minutes for the tcpO₂ reading. During this time the electrode will slowly heat the skin, making the arteries dilate. Longer time may indicate an incorrect attachment of the electrode or a poorly selected measuring site.

C. Anthropometric Measurements

Location of Procedure:

- Barnes-Jewish Hospital Operating Rooms
- Inpatient Hospital Units
- Other Hospital Units also housing vascular surgery patients

Measurements:

Measurements will be collected as long as the patient is hospitalized, including:

1. Temperature (daily maximum and minimum)
2. Blood Pressure Range

3. Heart Rate Range
4. SpO₂ Range
5. Respiratory Rate Range
6. Amputation wound assessment on POD 3 (if stump dressings are off and still hospitalized) and POD 5 (if stump dressings are off and still hospitalized).

In addition, a blood sample (~50mL; 3-4 table spoons) may be obtained for:

1. Hospital laboratory evaluations that may be obtained per standard of care, at standard of care time points during the hospital stay

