 1. CBC
 2. BMP
 3. HbA1C (Maybe obtained at some point during the course of the 6 day study if the patient did not have a value obtained within 3 month prior to the amputation)
 4. Pre-albumin (May be obtained at some point during the course of the 6 day study if the patient did not have a value obtained within 1 week prior to the amputation)
2. Research laboratory evaluation
 1. One sample within 12 hours from the time of the amputation operation, if possible
 2. One sample within 12 hours prior to discharge from the hospital or by POD5, if possible
 3. Samples will be taken to the research laboratory to evaluate:
 1. Serum Insulin level
 2. Serum Thiol Level
 3. Serum L-Cysteine level
 4. Serum lipidomics
 5. Serum nicotine and cotinine levels
 6. Other essential plasma/serum proteins or biomarkers

Contraindications to Measurement:

- Patient refusal/inability to participate in measurement before or at time of data collection (*a contraindication to anthropometric measurements does not exclude the patient from other measurements within the study protocol*).
- Severe anemia (Hematocrit < 22), that develops following enrollment in the study.

Data Analysis:

Anthropometric data will be analyzed to determine its effects on patient amputation stump healing score, qualitative peak perfusion, and/or quantitative peak perfusion.

D. MRI Measurements

Location of Procedure:

- Center for Clinical Imaging Research

Time of Data Collection:

- Postoperative Day 4, If possible and/or equipment available and if the patient is still in-house.

Contraindications to Measurement:

- Patient refusal/inability to participate in measurement before or during data collection
- Patient unable to lie supine for at least 30 minutes during measurement collection
- Contraindication to MR scanning such as intracranial vascular clips, pacemaker or intraocular metal.
- Patient is hemodynamically unstable, pregnant, are claustrophobic.

MRI Procedural Steps:

1. The patient is asked to lie supine on a narrow bed in the MRI scanner. An MRI scanner is a large donut-shaped machine that is used by thousands of hospitals to make pictures of various parts of the body. The patient is given ear plugs or earphones to dampen the loud noise the scanner makes when taking pictures. The patient is also given a squeeze ball which can activate an alarm at the scanner operator's console, so the patient can let the operator know to have a question or need assistance.

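### Refusing MRI when an arm has its three scans tells a study team that should stay blinded which patients share an arm

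*Combined protocol and SAP*

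**What the plan says.** The protocol section *Rationale for the Selection of Outcome Measures* plans MR perfusion at about POD 4 in six subjects, three on NAC and three on placebo. It promises: "The study team will continue to remain blinded to their study drug randomization". The study pharmacist tells that team which subjects may be scanned. The section gives an example: "if the MR perfusion portion of the study has already recruited 3 patients from the NAC group", and the fourth eligible patient is also allocated NAC, then "the pharmacy will notify the study team that the patient is not eligible for the MR perfusion study". No other ground for a pharmacy refusal is given, and nothing masks the notice. The same section says the scans are for research and do not guide care.

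Other sections bear on this:

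- *Randomization Method and Blinding*: "the patients will be randomized 1:1 by the BJH Investigational Pharmacy". No method or block size is given. The investigational team is denied access to the allocation record until the trial ends.
- *Treatment Regimen*: the pharmacy randomises from the medical record number, without the clinical history.
- *LAFA Procedural Steps*: "A member of the study team will obtain LAFA imaging of the stump". LAFA is scheduled on POD 0, 3 and 5.
- *C. Anthropometric Measurements*: "Amputation wound assessment on POD 3", and again on POD 5. *Visit 1* adds a stump evaluation 20 to 50 days after discharge. Neither names the assessor.
- *D. MRI Measurements*: the POD 4 scan is done "If possible and/or equipment available and if the patient is still in-house".

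**The concern.** The refusal depends on the treatment arm, and it is announced to the people who are supposed not to know the arm. The pharmacy randomises without clinical history, so its refusal can hardly be read as a contraindication; it points to a full arm.

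The notice must arrive by about POD 4 and may arrive at randomisation. The POD 5 LAFA, the POD 5 wound assessment and the post-discharge stump evaluation all come later, and they serve the two primary aims (perfusion and healing). An assessor who knows that certain patients are on the same treatment may score them alike. If a further clue names the arm, the scoring could favour one side. Stump assessment is more exposed than LAFA, which uses pre-set device settings.

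**Working it through.** **Inputs from the protocol.** Cap of 3 scans per arm, 6 in total; 1:1 allocation; 50 patients; interim analysis once more than 30 are enrolled. The plan gives no figure for this leak, so there is none to reproduce. The randomisation method and the share of patients who can be scanned are not stated and are varied below.

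**What a refusal reveals.** With fewer than six scans done, at most one arm can have three. Provided an accepted slot is not reopened:

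1. All patients refused before the sixth scan are in one arm.
2. All patients accepted after the first refusal are in the other arm.
3. If the first refusal follows exactly three scans, as in the protocol's example, those three and the refused patient all share an arm. After four scans the split is 3:1, so each earlier scanned patient is in the refused arm with probability 3/4. After five scans it is 3/5.
4. Refusals after the sixth scan reveal nothing.

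**Simple randomisation, all scannable (exact).**

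- P(no refusal) = C(6,3)/2^6 = 20/64 = 0.3125.
- First refusal after 3, 4 or 5 scans: 1/8, 1/4, 5/16. Sum = 11/16 = 0.6875.
- Mean number refused before the sixth scan: 15/8.
- Mean number accepted after the first refusal: 3(1/8) + 2(1/4) + 1(5/16) = 19/16.
- Patients who can be linked with certainty: 15/8 + 19/16 + 3(1/8) = 3.44. The last term is the first three scanned, when the first refusal follows exactly three scans.
- Linked already at their own notice: 15/8 + 19/16 - (1/4 + 5/16) = 2.5. A first refusal after 4 or 5 scans ties that patient to nobody identified until a later notice.

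**Other methods.** Fixed 25/25 list, all scannable: 1 - C(25,3)^2/C(50,6) = 0.667. Blocks of 4, all scannable: the first block is 2:2, and a refusal occurs unless the next two patients split 1:1 (probability 4/6), giving 1/3. The remaining entries were simulated (40,000 runs each).

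| Method (assumed) | Scannable | P(at least one refusal) | Linkable, of 50 | Linked at own notice |
|---|---|---|---|---|
| Simple | all | 0.69 | 3.44 | 2.50 |
| Fixed 25/25 | all | 0.67 | 3.07 | 2.19 |
| Blocks of 4 | all | 0.33 | 0.67 | 0.33 |
| Blocks of 2 or 6 | all | 0 | 0 | 0 |
| Simple | half | 0.69 | 3.44 | 2.50 |
| Fixed 25/25 | half | 0.67 | 3.07 | 2.18 |
| Blocks of 2, 4 or 6 | half | 0.57-0.58 | 2.0-2.1 | 1.4-1.5 |
| Simple | 30% | 0.69 | 3.34 | 2.41 |
| Fixed 25/25 | 30% | 0.67 | 3.05 | 2.16 |
| Blocks of 2, 4 or 6 | 30% | 0.62-0.63 | 2.6 | 1.8 |

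**Could the interim name the arm?** This needs exactly one arm full at 31 enrolled. Suppose MRI runs from the first patient, and let X and Y be the scannable patients per arm. Under simple randomisation with scannable share q, X and Y are each binomial(31, q/2), and the chance is 2[P(X ≤ 2) - P(X ≤ 2, Y ≤ 2)]. This is about 0% for q = 1, 1.7% for q = 0.5 and 24.8% for q = 0.3. The other methods give 0%, 0.6-0.9% and 20-22%. Only patients handled after the interim would be affected.

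**If slots reopen.** The protocol does not say whether they do. Simulation used simple randomisation, notice at randomisation, 10% to 30% of accepted patients not scanned, and one or two later patients entering before the scan result is known. Between 4% and 18% of those accepted after the first refusal are then in the refused arm. The inference becomes probable instead of certain.

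**The case against.** The strongest reply is that the notice never says NAC or placebo, so an assessor who knows only that a few patients share an unnamed arm has no direction in which to lean. The number grouped is small, from 0 to 2.5 of 50 at their own notice, and depends on unstated inputs. The first three scanned may be linked only after their POD 5 measurements. Nothing says that the person notified also images or scores the stump. The pilot has no power calculation and aims to estimate variance and correlation (*Statistical Methods*), and *Unblinding Procedures* already un-blinds the investigators at the interim. Finally, the example can be read as the fourth NAC patient, with placebo patients scanned in between.

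Much of this stands, and it limits the weight of the point. It does not remove it. The promise is to the whole study team, and nothing keeps the notice from those who assess outcomes. The leak can occur among the first patients, well before the interim. Zero under blocks of 2 or 6 requires every consecutive patient to be scannable, which the MRI section's own conditions make unlikely. The natural reading of the example is the fourth patient overall; on the other reading, the rule for refused and later accepted patients still holds.

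**Conclusion.** The concern holds. The MRI rule partly defeats the blinding that the same section promises. Under the methods examined, the chance of an informative refusal runs from 0% to 69%, and is about 57% to 69% if only half of the patients can be scanned. On average at most about 3.4 of 50 patients can be grouped, and about 5 when a refusal occurs under simple randomisation (3.44/0.6875).

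The notice reveals grouping, not the treatment; naming the arm needs a second clue. The likely bias is minor and ranks below the planned interim un-blinding. The point is worth correcting because the conflict is written into the protocol and the correction is cheap. The size rests on the assumed randomisation method and scannable share, and certainty of the grouping on slots not being reopened.

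**What to change.** Keep the three-plus-three cap. Amend *Rationale for the Selection of Outcome Measures* so that the pharmacy's eligibility notice goes only to a scheduler in the MR imaging group who does not read the scans, and to nobody who acquires or scores LAFA or assesses stump healing. Since the scans do not guide care, those people do not need the notice. State also whether a slot reopens when an accepted patient is not scanned.

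The cost is a short text change and one named recipient role; six scans and the 3:3 split are unchanged. Masking stays incomplete, because ward staff may see who is scanned. A missing scan would then have other explanations, such as a contraindication, equipment or discharge, and would no longer prove a refusal.

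If exact 3:3 is not essential, the pharmacy could instead flag at random equal numbers of NAC and placebo positions on the randomisation list, answer MRI yes or no from the flag alone, and stop after the sixth scan. This masks better but costs balance. With 5 + 5 flags, exact 3:3 occurs in C(5,3)^2/C(10,6) = 100/210 = 48% of cases; with 8 + 8, in C(8,3)^2/C(16,6) = 39%. With 5 + 5 flags, the chance of fewer than six scans, P(X ≤ 5) for X binomial(10, q), is 3%, 15% or 37% if 80%, 70% or 60% of flagged patients can be scanned.
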